6.4 Criteria for Withdrawal of Patients from Study

Participants have the right to withdraw from the study at any time and for any reason without prejudice to future medical care. In the case of participant withdrawal, the investigator will discuss with the patient the most appropriate way to terminate study participation to ensure the patient's health. All efforts will be made to complete and report the observations as thoroughly as possible up to the date of study termination. All applicable activities scheduled for the final study visit should be performed at the time of discontinuation. Randomized patients who withdraw from the study will not be replaced.

7. STATISTICAL CONSIDERATIONS

7.1 General Design Issues

COVET is a 3-arm prospective, multi-center, open-label, active comparator, randomized study designed to compare the efficacy and safety of apixaban and rivaroxaban compared with standard warfarin therapy. All potential study endpoints will be reviewed by a central adjudication committee that is blinded to treatment assignment. For participants who withdraw consent for follow-up, all data obtained prior to the time of formal withdrawal will be used in data analyses. The duration of follow up from randomization is expected to be twelve months, and all participants will be expected to remain in study until the 12-month follow-up telephone call regardless of whether they are taking their assigned study medication. Reporting of this prospective, randomized, open-label, blinded endpoint design will follow the CONSORT recommendations (Hansson 1992; Paggio 2012).

The primary efficacy endpoint is rate of recurrent VTEs and the primary safety endpoint is clinically relevant bleeding. Secondary endpoints include components of the primary endpoints, all-cause mortality, and other events of interest. The primary efficacy and safety endpoints will be confirmed by a CEC. Participants will be randomized in a 1:1:1 ratio to warfarin, apixaban, or rivaroxaban. Randomization will be stratified by the anticoagulant used during the screening period. For purposes of randomization, the screening anticoagulants will be classified as either warfarin, apixaban, rivaroxaban, or other. The relative open inclusion criteria, limited exclusions, and simple follow-up structure of COVET are an attempt to be pragmatic (Thorpe 2009).

SAS software version 9.4 or higher will be used for all statistical analyses. P-values less than 0.05 will be considered statistically significant unless otherwise specified. Complete details of all planned analyses will be contained in a separate Statistical Analysis Plan (SAP). The SAP will include the planned tables, listings, and figures. In particular, special attention will be given the participants who do not have complete data.

7.2 Sample Size Justification

The planning and sample size calculations for the COVET study were designed to compare warfarin vs. apixaban and warfarin vs. rivaroxaban. A direct exploratory and descriptive comparison of the two DOACs will be conducted but the study was not powered to detect statistically significant differences between those treatment groups.

For the primary safety endpoint, there will be two comparisons, apixaban versus warfarin and rivaroxaban versus warfarin, each of which will be tested at the two-sided 0.05 level of significance to detect a 50% reduction (HR=0.50) in clinically relevant bleeding compared to warfarin. For the primary efficacy endpoint, there will be two comparisons, apixaban versus warfarin and rivaroxaban versus warfarin to determine if the DOACs are non-inferior to warfarin in the prevention of recurrent venous thromboembolism. The non-inferiority assessments will be based on comparing the one-sided 95% upper confidence interval with a 2% absolute risk increase for recurrent VTE.

The type I error rates for the non-inferiority and superiority analyses have been set at 0.05 one-sided and 0.05 two-sided, respectively. These are considered standard values for two

arm studies. We have elected to not alter them for this three-arm design because the clinical questions of interest are the two comparisons of the DOACs versus warfarin.

For the primary efficacy analysis, using an outcome of recurrent VTE, we expect 12-month rate of 0.87% for the warfarin arm compared with 1.5% for the DOACs (Einstein Investigators 2010; Agnelli 2013). Sample sizes of 950 per arm are sufficient to provide 80% power to have the upper 95% one-sided confidence interval less than 2%. The proposed sample size of 1000 participants per arm allows for 5% missing data due to loss-to-follow-up, deaths not related to VTE, and lack of starting the assigned study drug. These calculations were obtained using a simulation method with nQuery Advisor 7.0 software.

For the primary safety analysis, the RE-MEDY study reported clinically relevant bleeding rates of 10.2% for the warfarin treated patients (Schulman 2013). Using a 12-month rate of 6.8%, a per group sample size of 950 participants (or 1000 / group with an allowance for 5% missing data) will provide greater than 90% power to detect a 50% event rate reduction for the DOAC arm. Similarly, assuming a lower 12-month event rate of 6.0% for the warfarin arm, the sample size of 950 participants per group will provide 88% power to detect a 50% event rate reduction for the DOAC arm. These calculations assume a two-sided 0.05 type I error rate and are based on a Cox model.

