1.3 Long-term prevention of recurrent VTE (after treatment of acute event)

Rivaroxaban and apixaban have each been compared to placebo for extended anticoagulation in patients who had completed 6 to 12 months of anticoagulation for the index VTE event (Einstein Investigators 2010; Agnelli 2013b). In both trials, extended anticoagulation treatment was for 12 months duration, the primary efficacy outcome was recurrent VTE and the primary safety outcome was major bleeding. In the Einstein-EXT RCT, 1200 patients were included and rivaroxaban was superior to placebo for preventing recurrent VTE (1.3% for rivaroxaban and 7.1% for placebo; HR, 0.18; 95% CI, 0.09 to 0.39) (cf. Table 1). Major bleeding events occurred in 0.7% of patients in the rivaroxaban group compared to no bleeding events in those on placebo. Clinically relevant bleeding (MB or CRNMB) events occurred in 6.0% of patients receiving rivaroxaban and 1.2% of those on placebo (cf. Table 2). The Amplify-EXT RCT compared two doses of apixaban (5 mg and 2.5 mg, twice daily) to placebo (Agnelli 2013b). Both doses of apixaban were superior to placebo in this trial of 2500 patients. The rates of recurrent VTE were 1.7% in each apixaban group compared to 8.8% in the placebo group (Table 1). Major bleeding events occurred in 0.2% in the 2.5 mg apixaban group, 0.1% in the 5 mg apixaban group, and in 0.5% of the placebo group. Clinically relevant bleeding (MB or CRNMB) events occurred in 3.2% of patients receiving apixaban 2.5 mg and 2.7% of those on placebo (cf. Table 2).

Table 1: Recurrent VTE event rates in Phase III VTE Secondary Prevention Trials

Study	Outcome	Comparator 1	Comparator 2	Hazard Ratio (95% CI)
RE-MEDY	Recurrent VTE or VTE-related death	Dabigatran: 1.2%	Warfarin: 0.87%	1.44 (0.78-2.64)
EINSTEIN-EXT	Recurrent VTE	Rivaroxaban: 1.3%	Placebo: 7.1%	0.18 (0.09-0.39)
AMPLIFY-EXT	Recurrent VTE or VTE-related death	Apixaban 2.5 mg BID: 1.7%	Placebo: 8.8%	Relative Risk: 0.19 (0.11-0.33)
AMPLIFY-EXT	Recurrent VTE or VTE-related death	Apixaban 2.5 mg BID: 1.7%	Apixaban 5 mg BID: 1.7%	Relative Risk: 0.97 (0.46-2.02)

Table 2: Clinically Relevant Bleeding (Major Bleeding [MB] and clinically relevant non-major bleeding [CRNMB]) event rates in Phase III VTE Secondary Prevention Trials

Study	Outcome	Comparator 1	Comparator 2	Hazard Ratio (95% CI)
RE-MEDY	MB or CRNMB	Dabigatran: 5.6%	Warfarin: 10.2%	0.54 (0.41-0.71)
EINSTEIN-EXT	MB or CRNMB	Rivaroxaban: 6.0%	Placebo: 1.2%	5.19 (2.3-11.7)

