AMPLIFY-EXT	MB or CRNMB	Apixaban 2.5 mg BID: 3.2%	Placebo: 2.7%	Relative Risk: 1.20 (0.69-2.10)
AMPLIFY-EXT	MB or CRNMB	Apixaban 2.5 mg BID: 3.2%	Apixaban 5 mg BID: 4.3%	Relative Risk: 0.74 (0.46-1.22)

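### Does the protocol's own 6.0% rivaroxaban bleeding rate undermine the power claimed for a 50% reduction?

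*Protocol*

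**What the plan says.** Protocol 7.2, repeated in SAP 7, sets one target for both DOACs: each comparison with warfarin is "tested at the two-sided 0.05 level of significance to detect a 50% reduction (HR=0.50) in clinically relevant bleeding compared to warfarin". It then notes that "the RE-MEDY study reported clinically relevant bleeding rates of 10.2% for the warfarin treated patients", but does not plan on that figure. The first scenario begins "Using a 12-month rate of 6.8%, a per group sample size of 950 participants" and claims power above 90%. The second reads "assuming a lower 12-month event rate of 6.0% for the warfarin arm, the sample size of 950 participants per group will provide 88% power". Neither document shows how 10.2% becomes 6.8%, or where the 50% comes from.

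The background rates are in Protocol 1.3. Of the rivaroxaban and apixaban extension trials it says "In both trials, extended anticoagulation treatment was for 12 months duration", and for rivaroxaban "Clinically relevant bleeding (MB or CRNMB) events occurred in 6.0% of patients receiving rivaroxaban and 1.2% of those on placebo". The bleeding table there (Table 2 of section 1.3) shows "Warfarin: 10.2" per cent for RE-MEDY and "Apixaban 2.5 mg BID: 3.2" per cent for AMPLIFY-EXT. No row has a time base, and the rivaroxaban row has no dose. Protocol 5.2 cites this table when it says that bleeding looks lower on the DOACs, and says that the trial is adequately powered to address the question.

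**The concern.** The table places a 10.2% warfarin rate next to DOAC rates from 12-month trials. Read at face value, rivaroxaban's 6.0% is a 41% reduction. Section 7.2, however, plans on a 12-month warfarin rate of 6.8%, exactly two thirds of 10.2%. Against that rate the same 6.0% is a reduction of only 12%. The baseline appears to have been put on a 12-month footing while the effect size was never checked there.

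Superiority of rivaroxaban over warfarin on bleeding is a primary safety objective. If the true effect were that small, the comparison would very probably miss significance, and readers might take the result as evidence of no difference. Apixaban does not raise the same worry, because its 3.2% is close to half of either planning rate.

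**Working it through.** **Inputs.** From Protocol 7.2: 950 per arm, two-sided 0.05, warfarin 12-month rate 6.8% or 6.0%, target HR 0.50. From Protocol 1.3: rivaroxaban 6.0%, apixaban 2.5 mg 3.2%, RE-MEDY warfarin 10.2%, and the RE-MEDY dabigatran-warfarin HR of 0.54 (0.41 to 0.71).

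**Formulas.** With 12-month risks p_w (warfarin) and p_d (DOAC):

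- HR = ln(1 − p_d) / ln(1 − p_w)
- expected events D = 950 × (p_w + p_d)
- power = Φ(|ln HR| × √(D/4) − 1.96) (Schoenfeld)

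**Step 1: the plan's own figures.**

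- 6.8% vs 3.4%: HR 0.491, D = 950 × 0.102 = 96.9, power 93.8%. Freedman's formula at HR 0.50 gives 90.7%. The stated value is above 90%.
- 6.0% vs 3.0%: HR 0.492, D = 950 × 0.090 = 85.5, power 90.6%. Freedman at HR 0.50 gives 86.9%, and a two-proportion test 88.4%. The stated value is 88%.

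Both claims reproduce.

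**Step 2: the tabulated DOAC rates against the planning rates.**

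| Warfarin vs DOAC | Ratio of rates | HR | Events | Power |
|---|---|---|---|---|
| 6.8% vs rivaroxaban 6.0% | 0.88 | 0.879 | 121.6 | 10.6% |
| 10.2% vs rivaroxaban 6.0% | 0.59 | 0.575 | 153.9 | 92.9% |
| 6.8% vs apixaban 3.2% | 0.47 | 0.462 | 95.0 | 96.5% |
| 6.0% vs apixaban 3.2% | 0.53 | 0.526 | 87.4 | 85.2% |

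At 1000 per arm the first row rises only to 11.0%. With 64.6 and 57.0 expected events, SE(ln HR) = √(1/64.6 + 1/57.0) = 0.182, so the expected 95% interval is about 0.62 to 1.25.

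**Step 3: the randomised contrast in the same table.** HR 0.54 on a 6.8% baseline gives p_d = 1 − 0.932^0.54 = 3.73%, D = 950 × 0.1053 = 100.0, power 86.9%. A hazard ratio estimated within one trial does not need the 10.2% to be put on a 12-month base.

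**Step 4: where power reaches 80%.**

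- Warfarin 6.8%, HR 0.575: p_d = 3.97%, D = 102.3, power 80%.
- Warfarin 6.0%, HR 0.55: p_d = 3.35%, D = 88.8, power 80%.

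**Step 5: the 10.2% and the 6.8%.** Under a constant hazard, 12 × ln(0.898)/ln(0.932) = 18.3 months. The two figures would fit together if 10.2% had accrued over about a year and a half. The documents give no RE-MEDY follow-up time, so this is inference only.

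**The case for a change.** The best case for a change does not rest on RE-MEDY at all. Protocol 1.2 gives two randomised rivaroxaban-warfarin comparisons: 8.1% in each group (ratio 1.00) and 10.3% against 11.4% (ratio 0.90). At 0.90 on a 6.8% baseline, power is about 8%. No section calls 50% the smallest effect worth finding, and the 0.54 belongs to dabigatran, which Protocol 1.4 leaves out of the trial. The pooled-rate review in Protocol 7.4 would not reveal a weak rivaroxaban effect: pooled bleeding would be (6.8 + 6.0 + 3.2)/3 = 5.3% against (6.8 + 3.4 + 3.4)/3 = 4.5% planned, so event numbers would look reassuring.

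Part of this stands. The documents give no rivaroxaban-specific basis for 50% and do not derive the 6.8%. If the true hazard ratio were near 0.9, the rivaroxaban comparison would have little power.

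The rest is weaker. The direct comparisons are in acute VTE, and Protocol 1.5 itself says that those trials carry over to extended treatment only to a limited degree. The 0.88 divides a rate from one trial by a planning rate attached to another. The placebo bleeding rates in the same table differ more than twofold (1.2% and 2.7%), so levels are not interchangeable between trials. The study arm is 10 mg daily, and the reader cannot tell whether the 6.0% belongs to that regimen. Section 7.2 states what the trial can detect on bleeding; only for recurrent VTE does it state what rates it expects. The statement in 5.2 that bleeding appears lower gives no size, and 6.0% is below 6.8%. A pooled review is meant to check event rates and cannot check a contrast between arms.

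**Conclusion.** No change is needed. The stated powers are right for a 50% reduction, so no figure in Protocol 7.2 or SAP 7 is in error. The 11% is the power at another effect, about HR 0.88. It holds only if the 6.0% applies to the study's rivaroxaban regimen and if rates can be compared across trials. The documents establish neither. The one randomised DOAC-warfarin hazard ratio for extended treatment that they cite, 0.54 for a drug outside the trial, gives about 87% power at 6.8%, so a class-based target near 0.50 has some support.

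What remains is thin justification: an unexplained step from 10.2% to 6.8%, unlabelled time bases, and one effect size for two drugs. Filling these gaps would leave enrolment, alpha, the non-inferiority margin, the models and the decision rules as they are. Protocol 7.5 and SAP 9.3.1 already call for a hazard ratio with 95% confidence interval for each DOAC against warfarin. If the rivaroxaban result is not significant, that interval (about 0.62 to 1.25 in the unfavourable case) will show how little has been excluded. A reader who wants to judge the design can use the thresholds above: 80% power needs a true HR of about 0.575 at a 6.8% warfarin rate, or 0.55 at 6.0%, assuming 950 evaluable patients per arm and proportional hazards.

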1.2 Preclinical Findings

The information on comparative effectiveness between rivaroxaban or apixaban and warfarin (target INR 2-3) is derived from industry-sponsored trials for treatment of acute VTE (Einstein Investigators 2010; Buller 2012; Agnelli 2013a). The duration of treatment in these trials was defined as the initial 3-12 months of anticoagulation after diagnosis of acute VTE. Einstein-DVT included nearly 3500 patients with proximal DVT and no symptomatic PE (Einstein Investigators 2010). Rivaroxaban was shown to be non-inferior to warfarin for the primary efficacy outcome of recurrent VTE with an event rate of 2.1% in the rivaroxaban arm and 3.0% in the warfarin arm (hazard ratio (HR), 0.68; 95% confidence interval (CI), 0.44 to 1.04). The

primary safety outcome was clinically-relevant bleeding, a composite of major bleeding or clinically-relevant non-major bleeding events, occurred in 8.1% of patients in each group. Einstein-PE enrolled 4800 patients with acute PE with or without DVT (Buller 2012). The primary efficacy and safety outcomes were identical to the Einstein-DVT trial. Rivaroxaban was similarly shown to be non-inferior to warfarin for the primary efficacy outcome with 2.1% of patients in the rivaroxaban arm versus 1.8% in the warfarin having recurrent events (HR 1.12; 95% CI, 0.75 to 1.68). Bleeding occurred in 10.3% of patients in the rivaroxaban group and 11.4% in the warfarin group. The Amplify RCT compared apixaban to warfarin in 5400 patients with acute VTE (Agnelli 2013a). The primary efficacy outcome of recurrent VTE occurred in 2.3% of patients in the apixaban group and 2.7% in the warfarin group (Relative risk (RR), 0.84; 95% CI, 0.60 to 1.18), demonstrating non-inferiority of apixaban to warfarin. The primary safety outcome of major bleeding occurred in 0.6% of patients in the apixaban group compared to 1.8% in the warfarin group, meeting pre-specified criteria for superiority.

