1.4 Clinical Experience with Study Agents

The standard oral anticoagulant that has long been used for extended treatment of VTE has been VKAs. Warfarin is the most common VKA available in North America and it is an effective anticoagulant that reduces the risk of recurrent VTE by >90% (Castellucci 2013). We have set the outcome of our comparative effectiveness study for superiority relative to warfarin. Despite its effectiveness, there are several limitations of warfarin use including the narrow therapeutic window, frequent INR monitoring to ensure patients remain in target range of 2-3, and many food and drugs interactions. The need to monitor INRs can be burdensome for patients and interfere with regular activities and functioning. DOACs have simplified anticoagulation treatment for many patients because they do not require laboratory monitoring for dosing adjustments. There are four DOACs available for treatment of VTE in the United States and Canada – dabigatran, edoxaban, rivaroxaban and apixaban. Edoxaban has not been studied for extended anticoagulation in VTE so we have excluded it from the trial. Dabigatran has been associated with higher rates of acute coronary syndromes in previous VTE trials and we excluded it from our proposed trial (Schulman 2012; Connolly 2009).

The DOACs rivaroxaban and apixaban were chosen as the intervention anticoagulants for the proposed trial. Rivaroxaban and apixaban are two Factor Xa inhibitors that are at least as effective and safe as warfarin for treatment of acute VTE (Einstein Investigators 2010; Buller 2012; Agnelli 2013a). Each DOAC has also been compared to placebo for extended anticoagulation in patients with VTE, demonstrating significantly lower rates of recurrent VTE and similar or lower rates of major bleeding events (Einstein Investigators 2010; Agnelli 2013b). The differences between the medications are in their dosing frequency as rivaroxaban is once daily and apixaban is twice daily. Both medications are currently approved by the FDA and Health Canada and are widely available from commercial pharmacies. Direct comparison of these anticoagulants to warfarin will enable us to determine whether they are as efficacious and as safe as warfarin for extended VTE treatment.

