2. OBJECTIVES AND ENDPOINTS

2.1 Primary Safety Objectives

In patients at high-risk for recurrent VTE, the COVET trial will

- Determine if apixaban is superior to warfarin, target INR 2-3, in the reduction of clinically relevant bleeding.
- Determine if rivaroxaban is superior to warfarin, target INR 2-3 in the reduction of clinically relevant bleeding.

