7.5 Data Analyses

Baseline characteristics will be presented using mean (standard deviation) and median (25th, 75th percentiles) for continuous variables and as frequencies (percentages) for categorical variables. No formal comparisons will be computed for baseline variables.

The primary analyses for safety primary endpoint will be based on an un-stratified Cox model adjusting for the two treatment indicators and three stratification indicators. The ascertainment time will be based on the time of the first event or censoring time. Stratification will be based on the anticoagulant used during the screening period. The all-randomized (ITT) analysis dataset will be used for the primary analyses. The treatment effect for each DOAC compared to warfarin will be computed using the estimated hazard ratio and associated 95% confidence intervals. Secondary analyses will be based on a Kaplan-Meier estimates on the all-randomized (ITT) and per-protocol populations.

For the efficacy primary endpoint, the primary analysis will be based on a Kaplan-Meier analysis using the all-randomized (ITT) analysis dataset. The 12-month event rates differences between the DOACs versus warfarin will be based on the difference in the Kaplan-Meier estimates and the one-sided upper 95% confidence interval will be based on a bootstrap estimator. Secondary analyses of the recurrent VTE endpoint will be based on the Cox regression model. Exploratory analyses will directly compare the two DOACs for both safety and efficacy endpoints. Additionally, an exploratory analysis will pool the two DOAC arms and compare those estimates with the warfarin treatment group.

For secondary endpoints, the estimated differences between the DOACs and warfarin treated groups will be based on linear models, logistic regression, and Cox models depending on the endpoint. Efforts will be made to limit the amount of missing data for the key endpoints and adherence measures. When necessary, multiple imputation will be used to account for missing covariate information.

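### Does the plan need a non-inferiority test for bleeding, because superiority sized for a halved rate is the only one planned?

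*Protocol*

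**What the plan says.** Protocol 2.1 gives two bleeding objectives, one per DOAC. The one for rivaroxaban reads "Determine if rivaroxaban is superior to warfarin, target INR 2-3 in the reduction of clinically relevant bleeding". The synopsis and SAP sections 3 and 6.1.1 say the same. Protocol 7.2 and SAP 7 describe the two comparisons, "each of which will be tested at the two-sided 0.05 level of significance to detect a 50% reduction (HR=0.50) in clinically relevant bleeding", and state the power: at a 6.8% warfarin rate, 950 per arm "will provide greater than 90% power to detect a 50% event rate reduction for the DOAC arm", and at 6.0%, 88%. Protocol 7.5 sets the reporting: "The treatment effect for each DOAC compared to warfarin will be computed using the estimated hazard ratio and associated 95% confidence intervals". Non-inferiority, with a margin of 2 percentage points, is planned for recurrent VTE only.

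Protocol 1.4 contains two sentences that pull in different directions. One says "We have set the outcome of our comparative effectiveness study for superiority relative to warfarin". The other says that comparing the drugs directly "will enable us to determine whether they are as efficacious and as safe as warfarin for extended VTE treatment".

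**The concern.** Read alone, the second sentence in 1.4 asks a question that a failed superiority test cannot answer: a confidence interval that includes 1 does not show equal safety. The efficacy half of that sentence has a matching non-inferiority test; the safety half has none.

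The documents also give reason to doubt that rivaroxaban halves bleeding. Protocol 7.2 cites a source for the warfarin rate but none for a hazard ratio of 0.50. In the acute DVT trial described in Protocol 1.2, clinically relevant bleeding "occurred in 8.1% of patients in each group". In the acute PE trial it was 10.3% on rivaroxaban and 11.4% on warfarin. If the true effect were small, the superiority test would probably fail, and any margin chosen afterwards would be post hoc. Non-inferiority followed by superiority on the same 95% CI costs no alpha within a comparison, so leaving it out can look like a missed opportunity.

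**Working it through.** **Inputs.** From Protocol 7.2: 950 evaluable patients per arm, warfarin 12-month rate p_w of 6.8% or 6.0%, two-sided 0.05, design HR 0.50. The non-inferiority margins M are assumptions, because the documents give none for bleeding.

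**Formulas.** DOAC rate p_d = 1 − (1 − p_w)^HR. Events E = 950 × (p_w + p_d). Superiority power = Φ(−ln HR × √(E/4) − 1.96). Non-inferiority power on the same CI = Φ((ln M − ln HR) × √(E/4) − 1.96).

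**The plan's own figures.**
- 6.8%: p_d = 1 − 0.932^0.5 = 3.46%. E = 950 × 0.1026 = 97.5. Φ(0.693 × 4.94 − 1.96) = Φ(1.46) = 93%.
- 6.0%: p_d = 3.05%. E = 85.9. Φ(0.693 × 4.63 − 1.96) = Φ(1.25) = 89%.

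A two-proportion calculation gives 92% and 88%. The stated values of greater than 90% and 88% are sound.

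**Superiority power at weaker effects.**

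| True HR | Warfarin 6.8% | Warfarin 6.0% |
|---|---|---|
| 0.50 | 93% | 89% |
| 0.54 | 87% | 82% |
| 0.60 | 74% | 69% |
| 0.70 | 47% | 42% |
| 0.80 | 23% | 20% |
| 0.90 | 8% | 8% |

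The 0.54 row is the dabigatran–warfarin hazard ratio in Protocol 1.3, the only extended-treatment comparison with warfarin that the documents report. The test reaches significance when the observed HR is at or below exp(−1.96 × 2/√E): 0.69 with about 110 events (6.8%), 0.67 with about 96 (6.0%). Power therefore falls below 50% only when the true HR is above about 0.67–0.69. An effect smaller than a halving does not by itself make failure the likeliest result.

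**What a non-inferiority step would give.** Take equal bleeding (HR 1.0), the case where an as-safe-as conclusion matters most. At 6.8%, E = 950 × 0.136 = 129 and √(E/4) = 5.68:
- M = 1.2: Φ(0.182 × 5.68 − 1.96) = 18%
- M = 1.3: Φ(0.262 × 5.68 − 1.96) = 32%
- M = 1.5: Φ(0.405 × 5.68 − 1.96) = 63%

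At 6.0% the same margins give 16%, 29% and 58%. For 80% power at HR 1.0, ln M must equal (1.96 + 0.84)/√(E/4), so M is about 1.64 (6.8%) to 1.69 (6.0%). The step needs no extra patients to write down, but at tight margins this sample does not power it.

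If non-inferiority also had to hold per protocol, fewer events would count. Assume 10% to 30% of events are lost, HR unchanged, M = 1.3, 6.8%. Per-protocol power at HR 0.80 is then 70% to 59%, against 75% with all events. At HR 0.90 it is 49% to 40%, against 53%.

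**The text side by side.** Protocol 2.1, the synopsis, and SAP 3 and 6.1.1 all state superiority for bleeding. Protocol 5.2 separates the two questions: for recurrent VTE, indirect evidence suggests the DOACs are no worse; for bleeding, rates look lower than on warfarin; the study is to address both. That matches non-inferiority for VTE and superiority for bleeding. The contrary reading rests on one phrase in 1.4, in a section that also says superiority was chosen.

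**The case for a change.** The strongest case for the concern is that the addition is cheap. Simulation confirms that, with non-inferiority read first and superiority second on one 95% CI, each claim has about a 2.5% error rate at its boundary, and superiority power is unchanged. At HR 0.80 and an assumed margin of 1.3, the chance of some formal favourable bleeding conclusion would rise from 20–23% to 69–75%. The doubt about rivaroxaban is also fair: its 6.0% extended-treatment bleeding rate in Protocol 1.3 is 0.88 of the planned 6.8% and equal to the planned 6.0%.

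These calculations stand, and so does the point that a non-significant superiority result must not be reported as equal safety. They do not make the plan wrong. The evidence for a weak effect is indirect: the two direct comparisons are in acute VTE, which Protocol 1.5 says generalizes poorly to extended treatment, and against the 10.2% warfarin rate in the extended-treatment trial the rivaroxaban ratio is 6.0/10.2 = 0.59. The gain depends on a margin that someone would have to choose and defend. A supporting per-protocol requirement would rest on comparisons that Protocol 7.5 itself says may not keep the validity of randomization. Reasonable statisticians could decide either way.

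**Conclusion.** The concern does not hold. The plan's bleeding question is whether each DOAC lowers bleeding. It tests that question, its power figures reproduce at 93% and 89% by the log-hazard-ratio approximation, and the hazard ratio with its 95% CI will show readers how much excess bleeding is excluded even if superiority fails. Lower power at weaker effects (69–74% at HR 0.60, 20–23% at 0.80) follows from the chosen target and is not an inconsistency. Adding non-inferiority would be a new confirmatory hypothesis, whose value at equal bleeding runs from 16% to 63% over the assumed margins of 1.2 to 1.5 and the two warfarin rates. What remains is one loosely worded background phrase in Protocol 1.4, which changes no analysis and no result. The figures assume proportional hazards, 950 evaluable patients per arm and the planned warfarin rates.
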